#### How should I take AMRIX?

- Take AMRIX exactly as your healthcare provider tells you to take it.
   Your healthcare provider will tell you how much AMRIX to take
- and when to take it.
- Your healthcare provider may change your AMRIX dose if needed.
- Take AMRIX around the same time every day.
   AMRIX should only be taken for short periods (up to two or three weeks)
- . If you take too much AMRIX, call your doctor or go to the nearest hospital emergency room right away.

# What should I avoid while taking AMRIX?

You should not drink alcohol until you know how AMRIX affects you. Taking AMRIX with alcohol or other medicines that depress your central nervous system can slow your thinking and physical response times.

Do not drive, operate machinery, or do other dangerous activities until you know how AMRIX affects you.

### What are the possible side effects of AMRIX?

AMRIX may cause serious side effects that may lead to heart attack or stroke. Call your healthcare provider right away or go to the nearest hospital emergency room if you have:

- irregular or abnormal heartbeats (arrhythmias)
- fast heartbeat (tachycardia)

Serotonin syndrome is a serious medical condition that may happen when AMRIX is taken with certain other medicines. Call your healthcare provider right away or go to the nearest hospital emergency room if you become severely ill and have some or all of

- these symptoms:

   agitation, hallucinations, coma, or other changes in mental status
- coordination problems or muscle twitching (overactive reflexes)
   fast heartbeat, high or low blood pressure
- · sweating or fever
- · nausea, vomiting, or diarrhea
- · muscle stiffness or tightness

The most common side effects of AMRIX include:

- · dry mouth
- dizziness
- · fatigue
- constipation
- nausea
- · upset stomach
- drowsiness

#### AMRIX® (cyclobenzaprine hydrochloride extended-release capsules)

Tell your healthcare provider if you get any side effect that bothers you or that does not go away.

These are not all the possible side effects of AMRIX. For more information, ask your healthcare provider or pharmacist.

Call your healthcare provider for medical advice about side effects. You may report side effects to FDA at [name].

#### How should I store AMRIX?

- Store AMRIX at room temperature, between 59°F to 86°F (15°C to
- Keep AMRIX in a tightly closed container, and keep AMRIX out of
- Keep AMRIX and all medicines out of the reach of children.

### General information about the safe and effective use of AMRIX.

Medicines are sometimes prescribed for purposes other than those listed in a Patient Information leaflet. Do not use AMRIX for a condition for which it was not prescribed. Do not give AMRIX to other people, even if they have the same symptoms you have. It may harm them.

This Patient Information leaflet summarizes the most important information about AMRIX. If you would like more information, talk with your healthcare provider. You can ask your healthcare provider or pharmacist for information about AMRIX that is written for healthcare professionals.

For more information, go to www.AMRIX.com or call [name].

### What are the ingredients in AMRIX?

Active Ingredient: cyclobenzaprine hydrochloride USP

Inactive Ingredients: diethyl phthalate NF, ethylcellulose NF (Ethocel Standard 10 Premium), gelatin, Opadry® Clear YS-1-7006, sugar spheres NF (20-25 mesh), and titanium dioxide.

#3, and FD&C red #40.

AMRIX 30 mg capsules also contain: FD&C blue #1, FD&C blue #2, FD&C red #40, and FD&C yellow #6.

# teva

Distributed By: Teva Pharmaceuticals USA, Inc.

North Wales, PA 19454

Manufactured By:

Adare Pharmaceuticals, Inc.

Vandalia, OH 45377

AMRPL-004

Revised: May 2018

© 2004-2018 Teva Pharmaceuticals USA, Inc.

All rights reserved.

AMR-40612

MedDRA	Medical Dictionary for Regulatory Activities	
Military-Related	Related to service in any branch of the armed services (active or veteran),	
	or as a military contractor	
MINI	Mini International Neuropsychiatric Interview	
MMRM	Mixed Model Repeated Measures	
N, n	Number (of participants)	
NEAE	Newly-Emergent Adverse Event	
NIH	National Institutes of Health	
PGIC	Patient Global Impression of Change Scale	
PROMIS	Patient-Reported Outcome Measurement Information System	
PTSD	Posttraumatic Stress Disorder	
REML	Restricted Maximum Likelihood	
SAE	Serious Adverse Event	

Protocol: TNX-CY-P306 Page 7 of 36 Final v1.0

SAP	Statistical Analysis Plan	
SAS®	Statistical Analysis System	
SD	Standard deviation	
SDS	Sheehan Disability Scale	
SDTM	Study Data Tabulation Model	
SE	Standard Error	
SL	Sublingual	
SOC	System Organ Class	
TEAE	Treatment Emergent Adverse Event	
TNX-102 SL	Cyclobenzaprine HCl sublingual tablets	
WHO-DD	World Health Organization Drug Dictionary	

Protocol: TNX-CY-P306 Page 8 of 36

Final v1.0

1. OVERVIEW

This Statistical Analysis Plan (SAP) describes the planned analysis and reporting for protocol TNX-CY-P306: A 40 to 52-Week Open-Label Extension Study to Evaluate TNX-102 SL Taken Daily at Bedtime in Patients with PTSD; Amendment 4, Dated 05JUN2019.

The structure and content of this SAP provides sufficient detail to meet the requirements identified by FDA, European Medicines Agency (EMA), and International Council for Harmonization (ICH) of Technical Requirements for Registration of Pharmaceuticals for Human Use: Guidance on Statistical Principles in Clinical Trials. All work planned and reported for this SAP will follow internationally accepted guidelines, published by the American Statistical Association and the Royal Statistical Society, for statistical practice.

The planned analyses identified in this SAP may be included in clinical study reports (CSRs), regulatory submissions, or future manuscripts. Also, post-hoc exploratory analyses not necessarily identified in this SAP may be performed to further examine study data. Any post-hoc, or unplanned exploratory analysis performed will be clearly identified as such in the final CSR.

The reader of this SAP is encouraged to also read the clinical protocol, and other identified documents, for details on the planned conduct of this study. Operational aspects related to collection and timing of planned clinical assessments are not repeated in this SAP unless relevant to the planned analysis.

For purposes of clarity, all analyses in this SAP refer to data collected in study TNX-CY-P306, except to the extent that some baseline measures may have been collected in a prior study (Section 7.1) and except for the analyses set forth in Section 12.

2. STUDY OBJECTIVES AND ENDPOINTS

2.1 Study Objectives

2.1.1 Primary Objective

The primary objective of the study is to evaluate the long-term safety of TNX-102 SL taken daily at bedtime over an additional 40 to 52 weeks in patients with PTSD who have participated in a double-blind lead-in HONOR study (TNX-CY-P301) and possibly a 12-week open-label extension study TNX-CY-P303.

Protocol: TNX-CY-P306 Page 9 of 36

Final v1.0

2.1.2 Secondary Objectives

The secondary objective of the study is to evaluate the long-term effect of TNX-102 SL taken daily at bedtime over an additional 40 to 52 weeks in patients with PTSD who have participated in a double-blind lead-in HONOR study (TNX-CY-P301) and possibly a 12-week open-label extension study TNX-CY-P303.

2.2 Study Endpoints

2.2.1 Efficacy Endpoints

Comparisons will be made at each study week of data collection to the baseline of this study.

Efficacy endpoints include:

- Average CGI-I score (scored 1-7)
- Proportion of patients with a CGI-I score of "very much improved" or "much improved"
- Change from baseline in the SDS total score
- Change from baseline in the individual items assessed using the SDS
- Change from baseline in patients' quality of sleep using the PROMIS Sleep Disturbance scale
- Change from baseline in BDI-II score
- Change from week 28 to week 40 in PCL-S
- Change from week 28 to week 52 in PCL-S (Track B subjects only)
- Change from week 40 to week 52 in PCL-S (Track B subjects only)

2.2.2 Safety Endpoints

Safety will be assessed by:

- Adverse events (AE) and serious AEs (SAEs) throughout the entire duration of the study, including detailed assessment of AEs involving the oral cavity.
- Changes from baseline in clinical laboratory test results.
- Changes from baseline in vital signs and weight.
- Change from baseline in BDI-II.
- Suicidal ideation or behavior as reported on the Columbia-Suicide Severity Rating Scale (C-SSRS).

Protocol: TNX-CY-P306 Page 10 of 36

Final v1.0

3. OVERALL STUDY DESIGN AND PLAN

This is a 40 to 52-week, multicenter, open-label extension study designed to establish long-term safety exposure and to examine the long-term effect with daily bedtime dosing of TNX-102 SL 5.6 mg (2 x 2.8 mg tablets) in patients with PTSD. This study will be conducted at approximately 35 sites in the United States (US).

Patients who have either: (a) completed the double-blind lead-in study (P301/HONOR study), and completed or are active (at the time of study discontinuation) in the 12-week open-label extension study, P303; or (b) are enrolled in the double-blind lead-in study (P301/HONOR study) that has been discontinued due to results of an interim analysis, will be eligible. For Track A patients, this extension study consists of 5 in-clinic visits, including the Screening/Baseline visit and visits after 7, 16, 28, and 40 weeks of treatment (Visits 3-6). There will also be a telephone visit after 2 weeks of treatment (Visit 2) for patients enrolling from the double-blind lead-in study, P301/HONOR. The total treatment duration of this study will be 40 weeks for patients enrolled under Track A criteria, and 52 weeks for patients enrolled under Track B criteria. Therefore, the maximum total duration of continuous treatment with TNX-102 SL could be approximately 64 weeks for those patients assigned to TNX-102 SL in the lead-in HONOR study who then also completed the 12-week open-label extension study P303. For patients enrolling from the open-label extension study, P303 (Track A), there is no need to repeat assessments at Visit 1 for this study, if the patient enrolls and initiates study treatment within fourteen days of completing the 12-week open-label extension study P303. For patients who are active in the double-blind lead-in study, P301/HONOR (Track B), all Baseline procedures and assessments will be completed at Visit 1.

After the patient has participated in the lead-in HONOR study or the open-label extension study, P303, and has consented to participate in this open-label extension study, patients will be dispensed a 7-week supply of open-label TNX-102 SL tablets (3 bottles) and will be instructed to take 2 tablets of study drug sublingually daily at bedtime, starting on the evening of Visit 1. A phone visit will be completed after 2 weeks of treatment for patients enrolling from the double blind lead-in study, P301/HONOR. All patients will return to the study center for safety and efficacy assessments at Weeks 7, 16, 28, and 40 (or early termination). Patients enrolled under Track B criteria will continue to dose for an additional 12 weeks and have the last study visit at Week 52. Patients will return their TNX-102 SL medication (including empty bottles) at these visits. Patients will also receive a 9-week supply of TNX-102 SL (4 bottles) at the Week 7 visit, and a 12-week supply (5 bottles) at the Week 16, 28 and 40 (Week 40 for Track B patients only) visits. Patients will be allowed to take other medications deemed appropriate by their health care providers to manage their PTSD and other conditions, including currently approved PTSD therapies.

3.1 Selection of Study Population

For a complete list of inclusion and exclusion criteria please refer to the protocol.

Protocol: TNX-CY-P306 Page 11 of 36

Final v1.0

3.2 Method of Treatment Assignment and Randomization

All patients will be assigned to TNX-102 SL, 5.6 mg regardless of which treatment arm they were randomized to in the lead-in study. No patients or site personnel will know what the prior treatment was in the double-blind lead-in study.

Throughout this document, when describing analyses performed by treatment group, this will refer to the treatment that the subject was randomized to in the double-blind lead-in study.

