#### Methodology:

This is an open-label, extension trial designed to evaluate safety of additional 40 to 52 weeks of TNX-102 SL 5.6 mg taken daily at bedtime for the treatment of PTSD. There are two possible "tracks" patients can use to enroll into this study:

Track A: patients that complete the double-blind lead-in HONOR study and complete *or are active (at the time of study discontinuation) in the* 12-week open-label extension study, P303, and received active drug in the 12-week double-blind lead-in study, P301/HONOR.

Track B: patients that are currently enrolled in the double-blind lead-in P301/HONOR study that has been discontinued due to results of an interim analysis *or are active (at the time of study discontinuation) in the* 12-week open-label extension study, P303, and received placebo in the 12-week double-blind lead-in study, P301/HONOR.

The study will consist of 5 or 6 in-clinic study visits, including Baseline Visit 1 (Day 0, which is anticipated to be the same visit as the last visit of the 12-week open-label extension study P303 for Track A patients), followed by in-clinic visits after 7, 16, 28 and 40 weeks of open-label treatment. Patients who are active in the 12-week double-blind lead-in study (P301/HONOR) at the time of enrollment to P306 will also have a 2-week phone check-in visit. All Track B patients will have 52 weeks of open-label treatment and a Visit 7. For patients enrolled from the discontinued double-blind lead-in study, P301/HONOR, the P306 Baseline Visit will occur in lieu of an early termination visit.

Patient safety parameters recorded at the final visit in the double-blind lead-in HONOR study (which is the baseline visit in the 12-week open-label extension study P303) can also be used as the baseline safety values for the P306 extension study for Track A patients. Patients will attend clinic visits at 7-, 9-, and 12-week intervals as indicated in the study visit schedule. Eligible patients who provide written informed consent will be provided with a supply of TNX-102 SL 2.8 mg tablets sufficient for

dosing until their next scheduled in-clinic study visit. At each clinic visit, patients will return their TNX-102 SL medication and will receive sufficient supplies to last them until the next scheduled visit. Patients will also have the option to have blood drawn for pharmacogenomic testing.

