## 6. INVESTIGATIONAL PLAN

## 6.1. Overall Study Design

This is a 40 to 52-week, multicenter, open-label extension study designed to establish long-term safety exposure and to examine the long-term effect with daily bedtime dosing of TNX-102 SL 5.6 mg (2 x 2.8mg tablets) in patients with PTSD. This study will be conducted at approximately 35 sites in the United States (US).

Patients who have either: (a) completed the double-blind lead-in study and complete, *or are active (at the time of study discontinuation)* in the 12-week open-label extension study, P303; or (b) are currently enrolled in the double-blind lead-in study (HONOR study) that has been discontinued due to results of an interim analysis, will be eligible. For Track A patients, this extension study consists of 5 in-clinic visits, including the Screening/Baseline visit and visits after 7, 16, 28 and 40 weeks of treatment (Visits 3-6). There will also be a telephone visit after two weeks of treatment (Visit 2) for patients enrolling from the double-blind lead-in study, P301/HONOR. The total treatment duration of this study will be 40 weeks for patients enrolled under Track A criteria, and 52 weeks for patients enrolled under Track B criteria. Therefore, the maximum total duration of continuous treatment with TNX-102 SL could be approximately 64 weeks for those patients assigned to TNX-102 SL in the lead-in HONOR study who then also completed the 12-week open-label extension study P303.

For patients enrolling from the open-label extension study, P303, there is no need to repeat assessments at Visit 1 for this study, if the patient enrolls and initiates study treatment within fourteen days of completing the 12-week open-label extension study P303. For patients who are active in the double-blind lead-in study, P301/HONOR, all Baseline procedures and assessments will be completed at Visit 1.

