## 9.4. Visit 6 (Week 40)

Visit 6 is to be conducted after 40 weeks ( $\pm 7$  days) of treatment in the extension study. At this visit, the patient (Track A only) will return all remaining study drug and the following assessments and procedures are to be completed in the following general order:

- Collect returned study medication from patient and perform drug accountability
- Assess study drug compliance
- Assess for occurrence of AEs
- Assess for changes in concomitant medications
- Obtain vital signs including weight
- Track A patients only: Draw blood for clinical laboratory tests
- For women of child-bearing potential, conduct urine pregnancy test
- Track A patients only: Inspect the oral cavity and document findings, if any
- Have the patient complete the PCL-S
- Have the patient complete the PROMIS-Sleep Disturbance Scale and SDS
- Have the patient complete the BDI-II
- Conduct the C-SSRS after reviewing the results of the BDI-II
- Conduct CGI-I comparing to the P306 baseline
- Track B patients only: Dispense 5 new bottles of TNX-102 SL tablets

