# 12.2. Evaluation of Efficacy

As this is a long-term safety study, minimal conclusions will be available concerning long-term efficacy. The efficacy analyses will focus on durability of the response achieved prior to entry into this extension study, based on the CGI-I for patients in Track A and for patients on active drug in the lead-in HONOR study or the P303-early-terminated patients (due to IA results) who were on placebo in P301 in Track B. In addition, durability of response for both Track A and B patients will be assessed by measuring the change in PCL-S scores from Visit 5 (Week 28) to Visit 6 (Week 40) in order to detect any potential worsening in PTSD symptoms as a result of longer term use of TNX-102 SL 5.6 mg. For Track B patients, an additional Visit 7 (Week 52) PCL-S assessment with be available for subset analysis of durability of response.

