7.2.1 Clinician Global Impression of Improvement (CGI-I)

The CGI-I will be completed by an Investigator to evaluate the participant's status since the start of the current study (P306). The CGI-I will be completed at each in-clinic visit after baseline. It will be the responsibility of the Principal Investigator or his qualified designee to assess change in the subject's overall status and answer the following question:

Since the initiation of treatment in P306, the participant is:

- 1 = Very much improved
- 2 = Much improved
- 3 = Minimally improved
- 4 =No change
- 5 = Minimally worse
- 6 = Much worse
- 7 =Very much worse

The primary analysis of CGI will treat it as a continuous variable (scored 1-7 as above). There will be an additional outcome presented where a responder on the CGI-I is defined a participant who is scored as 'Very much improved' or 'Much improved' and compared between the study arms.

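### SAP 3.2 says lead-in treatment stays unknown to sites, but for patients active in P303 at study discontinuation the protocol's track rule reveals it to the CGI-I rater by Week 40 at the latest

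*SAP*

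**What the plan says.** - **SAP 3.2** gives every patient the same drug and adds: "No patients or site personnel will know what the prior treatment was in the double-blind lead-in study". It then defines treatment group, throughout the SAP, as the randomised lead-in arm.
- **Protocol synopsis, Methodology** makes the track depend on that arm. Track A takes patients who finished the lead-in and completed, or were still active in, the "12-week open-label extension study, P303, and received active drug in the 12-week double-blind lead-in study, P301/HONOR". Track B takes patients still in the lead-in when it was stopped, and also those active in the "12-week open-label extension study, P303, and received placebo in the 12-week double-blind lead-in study, P301/HONOR".
- **Protocol 12.2** repeats the split, referring to "P303-early-terminated patients (due to IA results) who were on placebo in P301 in Track B". The same sentence appears to name lead-in active-drug patients for Track B as well.
- **Protocol 6.1** sets treatment at "40 weeks for patients enrolled under Track A criteria, and 52 weeks for patients enrolled under Track B criteria".
- **Protocol 9.4 (Visit 6)** has track-specific tasks: "Track B patients only: Dispense 5 new bottles of TNX-102 SL tablets" and "Track A patients only: Draw blood for clinical laboratory tests". Visit 7 (protocol 9.5) exists only for Track B.
- **SAP 3** labels P303 entrants Track A and patients active in P301 Track B. It does not mention the lead-in arm.
- **SAP 7.2.1** has the CGI-I scored by the principal investigator or a designee, with responders "compared between the study arms". SAP 9.1.1 estimates the between-arm difference by MMRM with a 95% CI, and SAP 9.1.2 adds a two-sided Z-test of proportions.

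**The concern.** The masking sentence allows no exception, yet the protocol uses the lead-in arm to decide how long some patients are treated. A site that knows where such a patient came from and which track the patient is on can work out the arm.

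The CGI-I is a judgement made at that site. SAP 7.2 lists it first, in approximate order of importance, and it is tested between the arms that the rater may be able to identify. A study report that carried SAP 3.2 forward would describe those comparisons as masked when, for a defined group, they are not.

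**Working it through.** This is a consistency check, so the main step is to set the texts side by side.

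**1. What the site knows about origin.** The Week 2 telephone visit is only for patients enrolled from P301 (protocol 9.1.5 and 9.2), and the Visit 1 assessments also differ by study of origin. Origin is therefore known from the start.

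**2. What the site knows about track.** At Visit 6 only Track B is dispensed more drug, and only Track A has laboratory tests and an oral inspection. The track is therefore evident by Week 40 at the latest. I found no provision for concealing it from sites, and none for an independent masked rater.

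**3. Origin and track combined, under the synopsis rule:**

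| Entry route | Lead-in active | Lead-in placebo | Does the track reveal the arm? |
|---|---|---|---|
| Direct from P301 | Track B, 52 weeks | Track B, 52 weeks | No |
| Active in P303 at discontinuation | Track A, 40 weeks | Track B, 52 weeks | Yes, with certainty |
| Completed P303 | Track A, 40 weeks | Unclear | Unclear |

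The last row depends on how the Track A sentence is read. If its active-drug condition covers completers, 40 weeks discloses active drug for them and placebo completers have no track. If it covers only P303-active patients, completers of both arms share Track A and nothing is disclosed.

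**4. Is the split a slip of wording?** The plan's own maximum reproduces: 12 + 12 + 40 = 64 weeks, as in protocol 6.1. Now take a patient k weeks into P303, with k < 12:
- lead-in active, then 40 weeks: 12 + k + 40 = 52 + k
- lead-in placebo, then 40 weeks: k + 40, which is below 52
- lead-in placebo, then 52 weeks: k + 52

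At k = 6 these are 58, 46 and 58 weeks. The two routes in the synopsis give equal total exposure of more than 52 weeks, which fits the synopsis aim of at least 52 weeks of exposure data for at least 50 patients. The split looks deliberate. A placebo completer given 40 weeks reaches 12 + 40 = 52, so this aim does not settle the completer row.

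**5. Size.** Let s be the share of patients who were active in P303 at discontinuation; the documents do not give it. Assume 1:1 lead-in allocation and no disclosure in anyone else (neither is stated). The chance that a site names the arm correctly is then s × 1 + (1 − s) × 0.5 = 0.5 + 0.5s:

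| s | Chance of naming the arm |
|---|---|
| 0% | 0.50 |
| 10% | 0.55 |
| 25% | 0.625 |
| 50% | 0.75 |
| 100% | 1.00 |

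**6. Source of the conflict.** SAP 1 says that the SAP follows protocol Amendment 4, but SAP 3 omits the arm-based split. SAP 13 lists only the study-day convention as a change.

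**The case against.** The strongest reply is that the synopsis is not the only account of the tracks. Protocol 6.1, 6.2 and 7.2 describe the entry routes without an arm condition. On the SAP 3 description the track says nothing about the arm, so SAP 3.2 agrees with its own design section. This stands to the extent that the root defect is an unreconciled track definition, and editing 3.2 alone would leave SAP 3 in conflict with the protocol. It does not rescue the sentence, because the synopsis states the rule expressly and protocol 12.2 relies on it.

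The consequence is also limited. The study is open-label with one drug, efficacy is secondary, protocol 12.2 expects minimal efficacy conclusions, and all p-values are nominal (SAP 7.1.1.1). That stands, and it lowers the importance of the point.

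A reader might infer more than the documents support:
- **That the whole CGI-I comparison is unmasked.** Patients entering directly from P301 are all Track B, so their track discloses nothing.
- **That every rating from Week 7 is affected.** Visits 3 to 5 have the same tasks for both tracks. Footnote a of protocol Appendix 1 uses track labels at baseline, but protocol 9.1.5 assigns the same tasks by study of origin. Knowledge before Week 40 is possible but not shown.
- **That patients can infer their own arm.** Nothing available shows that they are told the rule.
- **That restricting the analysis to P301 entrants gives a clean masked comparison.** In that subset lead-in placebo patients first take TNX-102 SL at the P306 baseline, while P303 entrants of both arms have already received it. The CGI-I is rated against that baseline, so the subset changes the question as well as the masking.

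**Conclusion.** The masking statement in SAP 3.2 is wrong as written for patients who were active in P303 at study discontinuation. For them, origin plus track identifies the lead-in arm to the site-based CGI-I rater by Week 40 at the latest. SAP 3 also conflicts with the protocol synopsis on how these patients are assigned.

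The conclusion rests on the synopsis rule being the one in operation and on sites applying the Visit 6 tasks as written. Disclosure through the track is complete for the P303-active group, nil for direct P301 entrants and undetermined for P303 completers. Its effect on the overall comparison cannot be sized without the P303-active share. The point is worth correcting because it changes how the secondary between-arm comparisons may be described. It does not touch the primary safety objective.

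**What to change.** 1. Reconcile SAP 3 and 3.2 with the protocol synopsis and protocol 12.2, and state how P303 completers are assigned. Say who assigns the track and when sites learn it. This point takes no view on what treatment duration any group should have.
2. Replace the absolute sentence in SAP 3.2 with one saying that, for patients active in P303 at study discontinuation, sites can infer the lead-in arm from the track.
3. Report the between-arm CGI-I comparisons, both the MMRM and the Z-test, as not masked for those patients.
4. Optionally, add a descriptive summary of the between-arm results by study of origin. Note that it is not a pure test of masking, for the drug-initiation reason given above.

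The cost is a few sentences, slightly more tabulation and a less favourable description of the secondary efficacy comparisons. Data collection does not change.
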